3 OBJECTIVES

3.1 Primary Objectives:

- To assess the safety of a single dose of two formulations of an MK-2048 vaginal film which is intended for extended release of antiretroviral drugs.

3.2 Primary Endpoints:

- Grade 2 or higher Adverse Events

3.3 Secondary Objectives:

- Pharmacokinetics: To describe the pharmacokinetics of MK-2048 drug at 0, 3, 5, 7, 10, 14, and 28 days after film insertion
- Acceptability: To describe the acceptability of two formulations of the MK-2048 vaginal film and identify qualities associated with higher or lower degrees of acceptability

3.4 Secondary Endpoint:

- MK-2048 concentrations in plasma, tissue homogenate, CVL, and rectal and vaginal swab eluents, comparing the two film types
- Acceptability: Self-reported assessment of qualities of the experience with the films drawn from existing survey on microbicidal films, and general acceptability ratings drawn from market research methodology

3.5 Exploratory Objectives:

- To compare the effects of two formulations of the MK-2048 vaginal film on the vaginal microbiota and glycome pre and post study product use
- To describe the pharmacokinetics of Eudragit® polymer to ensure that polymer persistence is proportional to drug release.
- To describe the protective effect of MK-2048 film against HIV in an *ex vivo* biopsy challenge model using cervical tissue

3.6 Exploratory Endpoints:

- Vaginal Microenvironment
 - Quantitative vaginal cultures and quantitative PCR for selected microbiota from vaginal swab
 - Nugent score from vaginal swab
 - Levels of anti-viral activity in CVL
 - Levels of glycoproteins and mucins in CVL
 - Levels of biomarkers of innate immunity in CVL
- Eudragit® pharmacokinetics
 - Eudragit® levels in CVL
- Ex vivo challenge: HIV infection of cervical tissue as measured by HIV-1 p24 replication by ELISA and confirmed either by immunohistochemistry or quantitative PCR assessment of integrated provirus in HIV-1 exposed cervical biopsies

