9.3.2 Secondary and Exploratory Endpoints

The secondary and exploratory endpoints of this study are as follows:

Secondary: MK-2048 pharmacokinetics

MK-2048 concentrations in plasma, tissue homogenate, and CVL rectal and vaginal swab eluents, comparing the two film formulations sampled at enrollment and post-enrollment time-points through Visit 8

Secondary: Acceptability

Reports of overall acceptability of the film and qualities of the experience with the film will be measured using a self-report survey drawing items from two sources. Overall acceptability is measured using standard language in market research methodology, each using a 5-point agreement scale followed by an open-ended explanation. Assessment of film-specific qualities of the experience is assessed by a 9-item scale drawn from previous research with participant-inserted films. Questions assess perceptions of leaking, vaginal dryness, and sensation of the film inside the vagina during and after insertion.

Exploratory: Vaginal Microenvironment

Given that there is no non-product use arm, participants will serve as their own control. Assessment of baseline microenvironment will take place during the Enrollment visit with the

exception of CVL properties. CVL will be obtained at the Screening visit so that the microenvironment can recover prior to study product administration at the enrollment visit.

Levels of lectin binding and mucins measured in CVL samples

Endogenous and exogenous glycolytic enzymes, formulated microbicide products, and microbial flora interact with mucins and may alter their structure and function. These alterations may be detected with lectins, which are sugar specific binding molecules, and can be bound to reporter molecules (such as horseradish peroxidase) in an ELISA type assay.

Nugent Score

Clinically significant changes in vaginal flora will be evaluated by a change in the Nugent score baseline (Visit 2, pre-exposure) through Visit 7. The Nugent score is graded 1 to 10 as follows:

Normal, 0 to 3

Intermediate, 4 to 6

BV, 7-10

Any shift from normal at baseline to intermediate or BV at Visit 3, 4, 5, 6, 7, or 8 or shift from intermediate or BV to normal at Visit 3, 4, 5, 6, 7, or 8 will be considered a scientifically meaningful change in vaginal microbiota.

Quantitative vaginal cultures and quantitative PCR

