Meaningful changes will be defined by greater than or equal to 1 log changes in dominant members of the microbiota, including *Lactobacillus* species, *Gardnerella vaginalis*, key anaerobic microorganisms, *Enterococcus* species, *Escherichia coli*, *Staphylococcus aureus*, Group B *Streptococcus*, and *Candida* species.

Levels of anti-viral activity in CVL

In-vitro anti-HIV activity will be determined by the TZM-bl assay.

The TZM-bl assay will determine HIV-1 infection by luciferase for single round of replication. To assess the potency of the CVL, serial dilutions will be made and tested to determine the IC₅₀.

Levels of biomarkers of innate immunity

Changes in cervical cytokine expression and innate immunity factors in cervicovaginal lavage will be assessed. Changes within each group will be reported. The factors to be analyzed will be determined on the scientific evidence at the time of the analysis.

Exploratory: Pharmacokinetic (PK)/ Persistence of Eudragit® in CVL

Persistence of polymer will be determined as detected levels of polymer in vaginal fluid collected through cervicovaginal lavage.

Exploratory: Ex vivo challenge

HIV infection of cervical biopsies as measured by HIV-1 p24 replication by ELISA and confirmation either by immunohistochemistry or quantitative PCR assessment of integrated provirus in HIV-1- exposed cervical biopsies.

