9.7.3 Secondary and Exploratory Endpoint Analysis

Summary statistics of frequencies and percentages will be provided for categorical data. Means and standard deviations or medians and ranges will be provided for continuous data. Methods for the analyses of the secondary endpoints are described below.

Student's t- and Mann-Whitney U tests will be used, where appropriate, to evaluate differences in the following continuous variables between the study arms: MK-2048 concentrations in plasma, rectal and vaginal swab eluents, and genital tissue, levels of glycoproteins and mucins in CVL, levels of cytokines and innate immunity factors, and antiviral activity in CVL. Between group pre- to post-exposure changes in the above endpoints will also be evaluated using Student's t- and Mann-Whitney U tests, where appropriate, while paired Student's t- and Wilcoxon signed-rank tests will be used to evaluate these changes within each study arm. Mixed effects linear regression will be used to evaluate associations between days of exposure to study product and these outcomes.

Nugent score will be categorized as follows: normal (score 0-3), intermediate (score 4-6), and bacterial vaginosis (score 7-10). Differences in the categorized Nugent score pre and post exposure levels will be evaluated using Fisher's exact, while McNemar's tests will be used to evaluate pre- to post-exposure shifts between normal (score 0-3) and abnormal (score 4-10) vaginal microflora within each study arm. Generalized estimating equations will be used to evaluate differences in the marginal post exposure prevalence of bacterial vaginosis between the two film formulations.

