Prevalence of microorganisms at each visit as assessed through culture and qPCR will be compared between the study arms using Fisher's exact tests, while pre- to post-exposure shifts will be evaluated within each group using McNemar's tests. Differences between the study arms in the quantity of microorganisms at each visit, as well as the change in quantity, will be evaluated using Mann-Whitney U tests. Meaningful changes will be defined by greater than or equal to 1 log changes in dominant members of the microbiota, including *Lactobacillus* species by quantitative PCR (qPCR), *Prevotella* species by qPCR, *Gardnerella vaginalis* (qPCR), *Atopobium vaginae* (qPCR) and *Megasphaera* phylotype I) qPCR). *Candida* species, facultative gram negative rods, staphylococci and streptococci will be evaluated by cultivation based methods. Fisher's exact tests will be used to evaluate differences in these changes between study arms. Mixed effects linear regression (for continuous outcomes) and generalized estimating equations (for binary outcomes) will be used to evaluate associations between days of exposure to study product and these outcomes.

Descriptive statistics will be performed for HIV infection of cervical biopsies as measured by HIV-1 p24 replication for each study arm and the combined cohort. Differences in HIV-1 p24 replication between study arms will be evaluated using Student's t-or Mann-Whitney U test, as appropriate.

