9.7.4 Analysis Cohort

The intent-to-treat cohort (ITT) will be defined as those who were randomized. It will be used for analyses of baseline characteristics, protocol deviations and violations, and trial conduct. The evaluable cohort (Eval) is a subset of ITT participants. Evaluable participants will be defined as participants who complete the Screening and Enrollment visits and return for their day 7 visit within the window for a safety assessment. Non-evaluable participants will be replaced.

TABLE 5: Statistical Analysis Plan

Endpoint	Variable	Statistics
Primary	Adverse Events	Frequency, Percent
	MK-2048 concentration	Mean, SD, Median, Range,
Secondary	Acceptability	Frequency, Percent

Exploratory	Persistence of Eudragit® in CVL defined as any concentration above the lower limit of quantification	Mean, SD, Median, Range
	Levels of glycoproteins and mucins, in CVL	Mean, SD, Median, Range
	Antiviral activity in CVL	Mean, SD, Median, Range
	Change in vaginal flora (Nugent score)	Frequency, Percent, Median, Range
	Culture/qPCR results from vaginal organisms - prevalence	Frequency, Percent
	Culture/qPCR results from vaginal organisms - concentration	Mean, SD, Median, Range
	Change in cytokine and innate immunity factors	Mean, SD, Median, Range
	HIV infection of cervical biopsies in ex vivo challenge	Mean, SD, Median, Range

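### Section 9.7.3 compares the films on level and on change (and, for organisms, on 1-log change), names none as the main comparison, and states none with the collected baseline as a covariate

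*Combined protocol and SAP*

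**What the plan says.** Section 9.7.3 sets out these between-arm analyses:

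- **CVL glycoproteins, mucins, cytokines and innate factors.** Levels are compared by Student's t or Mann-Whitney U. The text continues: "Between group pre- to post-exposure changes in the above endpoints will also be evaluated using" the same pair of tests.
- **Organism quantities.** Quantity at each visit, "as well as the change in quantity, will be evaluated using Mann-Whitney U tests". For changes of at least 1 log, Fisher's "exact tests will be used to evaluate differences in these changes between study arms".
- **Regression.** "Mixed effects linear regression will be used to evaluate associations between days of exposure to study product and these outcomes". The organism paragraph has a parallel sentence. Terms for arm and baseline are neither given nor excluded.

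Baselines exist. Section 9.3.2 says "Assessment of baseline microenvironment will take place during the Enrollment visit", with CVL as the exception, taken at Screening. Follow-up CVL is at Visits 7 and 8, and vaginal swabs are taken at Visits 3 to 8.

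Other text points both ways on level against change:

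- Section 9.3.2 makes each woman her own comparator for the vaginal microenvironment.
- The objective in Section 3.5 is "To compare the effects of two formulations of the MK-2048 vaginal film on the vaginal microbiota and glycome pre and post study product use".
- Sections 9.3.2 and 9.7.3 define a meaningful organism change as 1 log or more.
- For innate-immunity markers, Section 9.3.2 says "Changes within each group will be reported", which is within-arm reporting.
- Table 5 lists levels for glycoproteins and mucins, prevalence and concentration for organisms, and "Change in cytokine and innate immunity factors". It gives descriptive statistics only.

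None of this ranks the between-arm tests.

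**The concern.** Comparing the films on microbiota and glycome is a stated objective, and the plan gives two or three formal tests of it per outcome. Level and change differ in precision, and which is better depends on the pre-post correlation and the SD ratio, neither of which the documents give. If the tests disagree, the plan does not say which one answers the objective. If any significant result is read as a difference between the films, the error rate for that outcome exceeds 5%.

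The second issue is separate. A baseline is collected on every woman, but no stated between-arm analysis uses it as a covariate. Such an analysis stays close to the better of level and change without r having to be known.

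MK-2048 concentrations and CVL antiviral activity appear in the same sentences of Section 9.7.3. They are outside the precision argument here because their baselines are drug-free.

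**Working it through.** **The plan's own figures.** The only sample-size figures are exact 95% binomial bounds for adverse-event rates (Section 9.2). They reproduce: 0/48 gives an upper bound of 7.40% (stated 7.4%), 5/48 gives 22.66% (stated 22.6%) and 3/24 gives 32.36% (stated 32.4%). No power, SD, correlation or alpha is given for the outcomes discussed here.

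**Inputs.** From the documents: 48 women, 1:1, so 24 per arm, with non-evaluable women replaced. Assumed: two-sided 5%, a true difference of 0.8 post-exposure SDs, normal data, and a range of r.

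**Step 1: relative variance of the between-arm difference** (level = 1), with k = pre SD / post SD and N = 48:

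- change: 1 + k² − 2rk
- baseline-adjusted (ANCOVA): (1 − r²)(N − 3)/(N − 4) = (1 − r²) × 45/44

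**Step 2: power** from the noncentral t, with noncentrality 0.8/√(variance × 2/24). For level this is 0.8/0.2887 = 2.77. Degrees of freedom are 46, or 45 for ANCOVA. With k = 1:

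| r | Variance, change | Variance, adjusted | Power, level | Power, change | Power, adjusted |
|---|---|---|---|---|---|
| 0.3 | 1.400 | 0.931 | 77.4% | 63.0% | 80.3% |
| 0.5 | 1.000 | 0.767 | 77.4% | 77.4% | 87.2% |
| 0.7 | 0.600 | 0.522 | 77.4% | 93.8% | 96.4% |

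**Step 3: unequal SDs.** At r = 0.3, 0.5 and 0.7:

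- k = 1.5: change has 42, 54 and 72% power.
- k = 2/3: change has 76, 87 and 97% power.
- Adjusted power stays at 80, 87 and 96% in both cases. For k = 2/3 it therefore gains almost nothing over change from r = 0.5 up, and at r = 0.7 is marginally lower (96.4% against 96.7%).

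**Step 4: where adjustment loses to level.** (1 − r²) × 45/44 = 1 gives r = √(1/45) = 0.149. Below that, the worst case is r = 0, where variance is 45/44 = 1.023, a cost of about 2.3%. This is possible for CVL: Section 7.2 allows Screening up to 45 days before enrollment, and follow-up lavage is at days 14 and 28.

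**Step 5: false positives with no difference** (simulation, 24 per arm, r = 0.3 to 0.7), per outcome and visit:

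- either the level or the change t test significant: about 9%
- any of the two Mann-Whitney tests and the 1-log Fisher test (assumed SD 1.5 log10): 11-12%
- any single named test: about 5%

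**Step 6: every visit tested.** One test type at each visit, with equal correlation r between all visits:

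- six swab visits: adjusted about 22-25%, level alone about 17-24%, change alone about 20-21%
- two CVL visits: about 8-10% for each of the three

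**Step 7: disagreement.** The level and change t tests disagree on significance in about 22-28% of trials when the true difference is 0.8 SD, and in about 7-9% when there is none.

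**The case against.** The strongest reply is that these are exploratory outcomes in a phase I trial sized on adverse-event rates. No alpha is set for them, Table 5 is wholly descriptive, and reporting level and change side by side is ordinary at this stage. That stands, and it keeps the point minor. It does not remove it: Section 9.7.3 goes beyond description to formal between-arm tests of a comparative objective.

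It can also be said that the plan is not silent. The own-control statement, the pre-and-post objective and the 1-log rule favor change, and not only for cytokines. But Table 5 names levels for glycoproteins and mucins and concentration for organisms, so the signals conflict and set no order. Change scores do use the baseline, by subtraction; what is missing is a comparison with baseline as a covariate. The mixed models might contain arm and baseline terms, since their terms are not listed, but their stated purpose is association with days of exposure.

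A reader might infer that baseline adjustment would cut false positives steeply. If all three organism tests are run at all six visits, the simulated chance of at least one false positive per organism is 42-46%, against 5% for one adjusted contrast. That comparison is not like for like. It sets 18 tests against one, and Step 6 shows that adjusted tests at all six visits still give about 22-25%. The 5% comes from naming one test at one visit contrast. The text also does not clearly say that change and 1-log change are tested at every visit.

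Finally, all these figures assume normal data, whereas organism counts may include many undetected values. That limits the numbers to illustration and is a reason for a rank-based option.

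**Conclusion.** The point holds as a minor improvement. Section 9.7.3 leaves two between-arm comparisons for the CVL outcomes, and three for organism quantities, without a main one, and states none with baseline as a covariate.

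The case for adjustment is precision alone. Under the stated assumptions it gains 3 to 19 percentage points of power over level (r = 0.3 to 0.7). With equal SDs it gains 17, 10 and 3 points over change at r = 0.3, 0.5 and 0.7. The gain can vanish against change when the pre SD is the smaller, and turns into a small loss against level below r of about 0.15.

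The case for naming one comparison is that it restores 5% per outcome and visit, and this would be equally true of an unadjusted test. Disagreement between level and change is common only if a sizeable true difference exists.

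The documents do not support reading this as a threat to the trial's conclusions on safety. The primary endpoint, safety monitoring and N=48 do not depend on it.

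**What to change.** In Section 9.7.3, name one main between-arm comparison for each of these outcomes, adjusted for the collected baseline (Visit 1 for CVL, Visit 2 for swabs):

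- Use ANCOVA, or a repeated-measures model with formulation, visit, formulation-by-visit and baseline, on the log scale.
- Use a rank-based version where values are heavily skewed or often undetected, decided per outcome from pooled blinded data.
- Fix the visit contrast before unblinding.
- Label the level, change, 1-log and within-arm tests as supportive.

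The cost is SAP wording, one degree of freedom and a little analysis work, with no new samples, visits or participants. The change does not address multiplicity across outcomes. Section 9.7.3 names nine organism groups; at 5% each, and if independent, the chance of at least one false positive is still 1 − 0.95⁹ = 37%, so results should continue to be reported as exploratory.

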9.2 Sample Size and Accrual

The primary aim of the study is to assess the local and systemic safety of a single dose of two formulations of an MK-2048 vaginal film. The primary endpoint is the proportion of participants who experience a Grade 2 or higher adverse event. The proposed total sample size is N=48 divided into 2 arms (low and high Eudragit® content assigned at a 1:1 ratio). Based on previous studies of vaginal products conducted at the study site, the accrual of 48 eligible subjects with normal reproductive tracts is expected to require the screening of approximately 90 volunteers. Since unevaluable participants will be replaced, it is anticipated that 48 women exposed to study product will be evaluable for the primary endpoint.

The sample size is based on the exact binomial probability of observing Grade 2 or higher adverse events. **Table 4** gives the upper and lower bounds for the 95% exact binomial confidence intervals of the true Grade 2 or higher adverse event rate at all possible numbers of observed events in a group of size 24 or in the full cohort of 48. Note that the results for more than 50% of events in each group are not listed, but by symmetry can be calculated as 1- the listed rate and 95% CI for the number of non-events. If none of the 48 subjects experience Grade 2 or higher adverse events, the 95% exact 2-sided upper confidence bound for the Grade 2 adverse event rate is 7.4%. In a previous study of a single dose of the high Eudragit® content placebo film, 6 grade 2 adverse events were reported in a cohort of 64 women for an event rate of 9.4%. If similar event rates are observed in the proposed study, we will be able to rule out grade 2 or higher adverse event rates greater than 22.6% in the full cohort and 32.4% in each study arm.

TABLE 4: 95% confidence intervals for the true rate at all possible observed Grade 2 or higher adverse event rates

Number of observed events	Rate (95% CI)	Number of observed events	Rate (95% CI)
0/24	0 (0, 14.2%)	0/48	0 (0, 7.4%)
1/24	4.2% (0.1%, 21.1%)	1/48	2.1% (0%, 11.1%)
2/24	8.3% (1.0%, 27.0%)	2/48	4.2% (0.5%, 14.3%)
3/24	12.5% (2.7%, 32.4%)	3/48	6.2% (1.3%, 17.2%)
4/24	16.7% (4.7%, 37.4%)	4/48	8.3% (2.3%, 20.0%)
5/24	20.8% (7.1%, 42.2%)	5/48	10.4% (3.4%, 22.6%)

6/24	25.0% (9.8%, 46.7%)	6/48	12.5% (4.7%, 25.2%)
7/24	29.2% (12.6%, 51.1%)	7/48	14.6% (6.1%, 27.8%)
8/24	33.3% (15.6%, 55.3%)	8/48	16.7% (7.5%, 30.2%)
9/24	37.5% (18.8%, 59.4%)	9/48	18.8% (8.9%, 32.6%)

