9.6 Random Assignment

The randomization scheme will be generated and maintained by a member of the Data Management Center at the study site, and supplied to the Pharmacy. Women will be randomized to one of the two arms at a 1:1 ratio using a permuted block design with random block sizes of 2, 4, and 6. In order to minimize bias in group assignment, participants will be given study identification numbers. A study staff member will allot the identification numbers in sequential order as participants become eligible to enroll in the study. Numbered study film product packages will include sealed envelopes enclosing documentation of the randomized assignment to film formulation. The randomization scheme will be created for a total of 54 participants; the overage will be created to compensate for participant withdrawals or unusable products.

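### Section 9.7.3 tests the Nugent score only after cutting it; added full-scale tests would recover power, chiefly within arm, if a film shifts scores generally

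*Combined protocol and SAP*

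**What the plan says.** Section 9.7.3 names three Nugent analyses, all on a cut score:

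- "Differences in the categorized Nugent score pre and post exposure levels will be evaluated using Fisher's exact", with categories 0-3, 4-6 and 7-10. The sentence does not say whether the comparison is between arms or between time points.
- Within each arm, "McNemar's tests will be used to evaluate pre- to post-exposure shifts between normal (score 0-3) and abnormal (score 4-10) vaginal microflora".
- GEE on post-exposure prevalence of bacterial vaginosis (BV), comparing the two films.

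The score is absent from the section's list of continuous variables given t, Mann-Whitney, signed-rank or mixed-model tests. Table 5 summarises it by frequency, percent, median and range.

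Section 9.3.2 opens the endpoint with "Clinically significant changes in vaginal flora will be evaluated by a change in the Nugent score". It then defines the change that counts: a move between normal and intermediate or BV, in either direction, at any of Visits 3 to 8.

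For organism quantity, section 9.7.3 keeps a cut (a change of at least 1 log, compared by Fisher's exact test) and also tests the full scale: the quantity at each visit, "as well as the change in quantity, will be evaluated using Mann-Whitney U tests".

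**The concern.** An exploratory objective (section 3.5) is to compare the two films' effects on the vaginal microbiota before and after use. There is no untreated arm, so section 9.3.2 makes each woman her own control, and the within-arm paired test carries much of the weight. Asymptomatic BV is not counted as an adverse event (section 8.3), so the flora measures, not the primary endpoint, have to show it.

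A cut score registers only boundary crossings. A move from 0 to 3, or from 4 to 6, is invisible to the McNemar test, and a move from 2 to 6 is invisible to the BV model. With 24 women per arm, a general drift in one film could go undetected on the Nugent tests although the collected score would show it.

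**Working it through.** **The plan's own figures.** No power, effect size or significance level is given for any Nugent test. The sample size rests on the "95% exact binomial confidence intervals of the true Grade 2 or higher adverse event rate". Those limits reproduce: for 0/48 the upper limit is 1 − 0.025^(1/48) = 7.4%; for 3/24 it is 32.4%; for 5/48 it is 22.66% (printed as 22.6%). So 24 per arm was not chosen with a flora comparison in mind.

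**Inputs from the documents.**
- "The proposed total sample size is N=48 divided into 2 arms" (section 9.2).
- "Women will be randomized to one of the two arms at a 1:1 ratio" (section 9.6), hence 24 per arm.
- "Non-evaluable participants will be replaced" (section 9.7.4), so no dropout is deducted.
- Cut points as above.

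**Assumptions, because the documents give none.** Two-sided 5% level, and two sets of score distributions:
- Set A: underlying normal scores, mean 1 to 3 and SD 3 to 4, rounded and limited to 0-10 (26-44% abnormal at baseline); within-woman correlation 0.5 to 0.7; shift of 1.5 or 2 points on the underlying scale.
- Set B: baseline 65% normal, 20% intermediate, 15% BV; correlation 0.5 to 0.85; shift of about 1.3 to 2 points in the mean recorded score.

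**Step 1: what the cut tests need, with no distribution assumed.**
- Exact McNemar with k women all crossing the same way: p = 2 × 0.5^k. For k = 5, p = 0.0625; for k = 6, p = 0.031. At least 6 of 24 must cross.
- Uncorrected chi-square McNemar, (b − c)²/(b + c): four one-way crossings give 16/4 = 4.0, above 3.84; three give 9/3 = 3.0. At least 4 must cross.
- Fisher's exact at one visit, yes/no outcome, 0/24 v 5/24: p = 2 × C(24,5)/C(48,5) = 2 × 42,504/1,712,304 = 0.0496. This is the smallest significant split from zero.

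**Step 2: within arm, general shift (simulated power).**

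| Assumptions | Exact McNemar | Chi-square McNemar | Wilcoxon on change |
|---|---|---|---|
| A, 1.5 points | 11-28% | 19-43% | 33-80% |
| A, 2 points | 22-51% | 33-66% | 55-97% |
| B, about 1.3-2 points | 20-64% | 29-83% | 50-100% |

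Case by case in set A, Wilcoxon leads chi-square McNemar by 14 points (0.330 − 0.189) to 37 points (0.801 − 0.431), and exact McNemar by 22 (0.330 − 0.110) to 52 (0.790 − 0.266). With no shift, rejection rates were 0.7-1.9% (exact McNemar), 4-5% (chi-square McNemar) and 4-5% (Wilcoxon). Part of the gap to the exact version is therefore its conservatism.

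**Step 3: between films, one visit.** In set A, three-category Fisher against Mann-Whitney on the uncut post-dose score differs by 10 points (0.223 − 0.124) to 22 points (0.574 − 0.358). The set B baseline with a shift of about 1.7 points separates the effect of the cut from the effect of using Visit 2:

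| Correlation | Fisher, 3 categories | Mann-Whitney, post-dose score | Rank ANCOVA on Visit 2 score |
|---|---|---|---|
| 0.5 | 28% | 48% | 61% |
| 0.7 | 32% | 52% | 72% |
| 0.85 | 31% | 49% | 92% |

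Uncutting adds 20, 20 and 18 points. Using the Visit 2 score adds a further 13, 20 and 43. The last column comes from a separate run, so these second differences are approximate.

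**Step 4: between films, six visits pooled.** The stand-in for the GEE is a t test on each woman's mean over six visits (set A, 2 points): BV yes/no 31-70%, score 46-84%. At 1.5 to 2 points the loss is about 10 to 25 points. Most of it comes from cutting at BV: pooling normal v abnormal instead loses only 2 to 8 points (for example 0.279 − 0.254 and 0.733 − 0.657).

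**Step 5: women only flip between categories.** Within arm, with 25% crossing: exact McNemar 58%, chi-square McNemar 90%, Wilcoxon 77%. Between films differing only in category mix: normal/abnormal Fisher 49-75%, chi-square 60-83%, Mann-Whitney 48-79%. The full-scale advantage shrinks, vanishes or reverses.

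**The case against.** The strongest defence is that section 9.3.2 says which change matters, namely crossing between normal and abnormal, and the McNemar test addresses exactly that event. On that definition a move from 0 to 3 is not meaningful, and preferring the full scale changes the question. This largely stands, and it is why the planned tests should stay. It does not cover the whole plan. The GEE, the only Nugent test explicitly assigned to comparing films, uses BV rather than the normal/abnormal boundary, and no adjustment for Visit 2 is stated. For organism quantity the same section pairs a defined meaningful change with a full-scale test, so the two can coexist.

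Other parts of the defence also stand:
- The GEE pools visits, which recovers some power.
- The plan does not say which McNemar version is meant. The chi-square version narrows the gap without closing it under a general shift.
- Table 5 would show a drift in the median, though without a test.

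A reader might infer that flora changes as a whole are tested weakly. They are not: culture and qPCR quantities and their changes are tested uncut by Mann-Whitney, with mixed models over days of exposure. A reader might also infer that cutting always discards most of the information. Step 5 shows a plausible pattern in which it costs nothing, and the documents give no Nugent distribution from which to choose between patterns.

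**Conclusion.** The concern holds as a minor point about one exploratory endpoint. No planned test uses the Nugent score or its change from Visit 2, although the score is collected at Visits 2 to 8.

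The cost depends on how scores move. Under a general shift it is clear within arm, even against chi-square McNemar. Between films at one visit the cut alone costs roughly 10-20 points, and the larger gains come from using Visit 2. If change is purely crossing between categories there may be no cost. All power figures rest on the stated assumed distributions and a 5% two-sided level.

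It would be tempting to conclude that the full-scale score should replace the categorical tests. That does not follow: it would leave the plan's own meaningful change untested. Nor do the documents show that a non-significant Nugent result would be taken as evidence of safety. The sample size, the primary endpoint and the secondary endpoints are untouched.

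**What to change.** Keep the planned Fisher, McNemar and GEE analyses, and add to section 9.7.3:

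- Within each arm, a Wilcoxon signed-rank test on change in Nugent score from Visit 2, at a named post-dose visit.
- Between films, a rank-based comparison of the post-dose score adjusted for the Visit 2 score. Acceptable alternatives are Mann-Whitney on the change, or an ordinal or mixed repeated-measures model across visits.

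In the same edit, say whether the Fisher sentence compares arms or time points, and which McNemar version is meant. Tidy section 9.3.2, which grades the score from 1 but starts the normal range at 0, and ends follow-up at Visit 7 in one sentence and Visit 8 in another.

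The cost is a few lines of text and code on data already collected, settled before unblinding. The downsides are small: a few more exploratory tests, and a score shift that is less directly clinical than a category change. The retained categorical analyses cover the second.
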